2. STUDY OBJECTIVES AND ENDPOINTS

2.1 Study Objectives

2.1.1 Primary Efficacy Objective

The primary objective is to assess whether subjects randomized to receive RHB-104 have a higher probability of being in a state of remission (CDAI score <150) at week 26 assessment as compared to subjects randomized to receive placebo.

2.1.2 Key Secondary Efficacy Objectives

1. Assess whether subjects randomized to receive RHB-104 have a higher probability of being in a state of response at the 26 week assessment as compared to subjects randomized to receive placebo.
2. Assess whether subjects randomized to receive RHB-104 have a higher probability of being in a state of remission at the 52 week assessment as compared to subjects randomized to receive placebo.
3. Assess whether subjects randomized to receive RHB-104 have a higher probability of being in a state of durable (long-term) remission in assessments from week 26 through week 52 as compared to subjects randomized to receive placebo.
4. Assess whether subjects randomized to receive RHB-104 have a higher probability of being in state of early remission at the 16 week assessment as compared to subjects randomized to receive placebo.
5. Assess whether subjects randomized to receive RHB-104 have a higher probability of being in a state of steroid free remission at the 52 week assessment as compared to subjects randomized to receive placebo. Subjects must be maintained off steroids for 3 weeks in order to be determined to be in steroid free remission, e.g., by week 49.

2.1.3 Other Supportive Secondary Efficacy Objectives

1. To compare the arm-specific time to remission and time to response.
2. To compare the arm-specific duration of remission and duration of response.
3. To compare the proportion of subjects who have maintained remission from week 16 through week 52.
4. To assess whether subjects randomized to receive RHB-104 have a higher probability of being in a state of response at the 16 week assessment as compared to subjects randomized to receive placebo.
5. To assess the difference between the treatment groups in health-related quality-of-life using the IBDQ and SF-36 questionnaire instruments.
6. To compare arm-specific endoscopic 26-week changes using the CDEIS and SES-CD score in those subjects who consent to undergo colonoscopy.
7. To assess the effect of RHB-104 on markers of inflammation.
8. To assess the proportion of subjects in steroid free remission in each treatment arm at week 26. Subjects must be maintained off steroids for 3 weeks in order to be determined to be in steroid free remission e.g. by week 23.

2.1.4 Other Exploratory Efficacy Objectives

1. To characterize the pharmacokinetic profiles of each of the active agents (and active metabolites for clarithromycin and rifabutin) using a population PK approach.
2. To assess the efficacy outcome measures for interaction with the baseline assay results for MAP infection (positive versus negative) to use in development of MAP blood PCR testing.
3. To compare the arm-specific changes in MAP PCR status (positive to negative) from pre- to post-treatment at week 26 and week 52.
4. To compare arm-specific 26-week change from baseline in the endoscopic index (Δ CDEIS and Δ SES-CD) and the clinical index (Δ CDAI)
5. To compare the arm-specific changes in MAP culture status (positive to negative) from pre- to post-treatment at week 26 and week 52.
6. To assess the tissue levels of the active agents of RHB-104 in colon biopsy samples if possible.

2.1.5 Safety Objective

Assess the safety impact of treatment with RHB-104.

2.2 Outcomes/Endpoints

The efficacy endpoints for statistical comparison between the RH-104 treatment and Placebo are grouped into 4 families for statistical analysis: (i) Primary efficacy endpoint; (ii) Key Secondary efficacy endpoints; (iii) Other Supportive Secondary efficacy endpoints; and (iv) Other Exploratory efficacy endpoints. The endpoints in families (i) and (ii) that are for potential treatment efficacy labeling claim will have multiplicity adjustment to control type 1 error rate.

2.2.1 Primary Efficacy Endpoint/Variable: Remission

In general use of rescue medication is considered as treatment failure (not achieve remission or response) if there are any new use of rescue medication to treat CD or increased rescue medication dose from baseline prior to any remission or response assessment. Please refer to section 6.1.8 for more details.

The primary efficacy variable is the proportion of subjects experienced remission at Week 26, where remission is defined as a subject having a Crohn's Disease Activity Index (CDAI) score of <150 . Subjects who have a Week 26 CDAI measurement ≥ 150 or who do not have a CDAI measurement at Week 26 will be classified as not achieved remission.

The CDAI is used to assess the activity of CD; higher scores indicate more active disease.

2.2.2 Key Secondary Efficacy Endpoints/Variables

Key Secondary efficacy endpoints include the following:

- Proportion of subjects experienced response at week 26, where response is defined as reduction from baseline of ≥ 100 in CDAI score. Subjects who have a change from baseline to week 26 in CDAI score which is not a reduction of ≥ 100 or who do not have a change from baseline to week 26 in CDAI score will be classified as not experienced response.
- Proportion of subjects in remission Week 52, where remission is defined as a subject having a CDAI score of < 150 . Subjects who have a week 52 CDAI measurement ≥ 150 or who do not have a CDAI measurement week 52 will be classified as not achieved remission.
- Proportion of subjects experienced Durable Remission (CDAI score < 150) from week 26 through week 52. Subjects experiencing a CDAI score ≥ 150 at any visit time point assessment between week 26 and week 52 or have no CDAI measurement week 26 or week 52 will be considered not achieved Durable Remission.
- Proportion of subjects in Early Remission week 16, where remission is defined as a subject having a CDAI score of < 150 . Subjects who have a week 16 CDAI score ≥ 150 or who do not have a CDAI measurement week 16 will be classified as not achieved early remission.
- Proportion of subjects in steroid free remission week 52, where remission is defined as a subject having a CDAI score of < 150 . Subjects must be maintained off steroids for 3 weeks in order to be determined to be in steroid free remission, e.g., by week 49.

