6.1.5 Missing Data and Handling of Dropouts

All available efficacy and safety data will be included in data listings and tabulations. All patients who prematurely discontinue for any reason will be considered failures for the different proportion based endpoints.

CDAI Missing Data:

Final Version 3.0, 05 April 2018

The computation of CDAI requires 7 days of consecutive diary daily data. For subjects with CDAI diary data reported that is less than 7 days of data, the reported data will be standardized to 7 days by dividing the sum of CDAI score over the number of days of data by total number of days of reported data multiplied by 7. If less than 4 days of diary data is available, the subject will be categorized as a non-responder and the CDAI score will be considered missing. As specified in the protocol, subjects with missing week 26 assessment will be assumed to not be in a state of remission at week 26 (i.e., non-responders). Similarly, for subjects with missing week 52 assessments will be assumed not to be in state of remission at week 52. Sensitivity analyses may be performed on Observed Case (completer analysis) only.

Handling of missing date information for AEs:

The term *missing date* refers to a completely missing date or to partial date where month or/and day or/and year is/are missing, e.g. missing month/day/year. Missing start and end dates will be imputed conservatively, i.e. missing values will be imputed in such a way that the duration of the AE is considered with the longest possible duration. The missing start date and end date of AE will be imputed for the purpose of defining treatment emergent adverse events (TEAE) and for assigning events to treatment periods using the following definitions:

(i) Adverse Event Start Date:

Event Missing Day: If Adverse event day is missing but month and year present, then impute the 1st of the month unless month and year are the same as first dose of study drug then impute day first day of dose.

Event Missing day and month – If adverse event day and month both are missing but year is present then impute 1st January unless year is the same as first dose date then impute day and month first dose day and month.

Completely missing – impute first dose date unless the end date suggests it could have started prior to this in which case impute the 1st January of the same year as the end date.

(ii) Adverse Event End Date:

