6.3.1 Primary Efficacy Analysis

The primary efficacy analysis will be performed on ITT population. Sensitivity analyses may be performed on Observed Case (completers only), on subjects with no violation of key inclusion/exclusion criteria (mITT population), and on PP population.

The primary efficacy variable is the proportion of subjects experienced remission week 26, where remission is defined as a subject having a Crohn's Disease Activity Index (CDAI) score of < 150 . Subjects who have a week 26 CDAI measurement ≥ 150 or who do not have a CDAI measurement week 26 will be classified as not achieved remission. The primary analysis will compare the RHB-104 treated group to Placebo treated group on ITT population using Cochran-Mantel-Haenszel (CMH) chi-square test controlling for the stratification variable anti-TNF agents use (yes/no). The null and alternative hypotheses are as follows, where π_R and π_P are the proportion of subjects with remission in the RHB-104 and placebo treated groups, respectively.

Null hypothesis $H_0: \pi_R = \pi_P$

"Proportion (%) of subjects in Remission in RHB-104 Treatment is equal to Proportion (%) of subjects in Remission in Placebo Treatment at week 26"

Alternative hypothesis $H_1: \pi_R \neq \pi_P$

"Proportion of subjects in Remission for RHB-104 Treatment is not equal to Proportion of subjects in Remission for Placebo treatment at week 26"

For each treatment group, descriptive statistics will be presented including the number of observations, proportion (%) of subjects in remission.

The primary analysis will compare RHB-104 group to the placebo group using a two-sided test at the $\alpha = 0.049$ level of significance.

The statistical criterion for primary objective success will be met if the CMH chi-square test p-value comparing the RHB-104 arm with the placebo arm (Higher proportion in RHB-104 than placebo) is less than 0.049 based on a 2-sided test taking into account the pre-specified protocol alpha spent at interim equal to 0.003.

For each treatment group, parameter estimates with 95% confidence interval will be presented including the number of observations and proportion (%) of subjects in remission.

To assess the robustness of the primary results, sensitivity analysis will be performed on mITT and on observed case (only completers with 26 weeks of data). The observed case population will include only subjects that have 26 weeks assessment.

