6.3.2.3 Durable (or Sustained) Remission

This analysis is intended to compare the two treatment groups considering only the subjects that experienced remission (CDAI < 150 score) week 26 through week 52 (Sustained Remission). Subjects who are not in remission at any visit point assessment between 26 and 52 weeks will be considered as non-responders for this analysis. The same statistical method as used for the primary endpoint will be used for this analysis. The proportion (%) of subjects experienced sustained remission will be summarized for each treatment group and compared between the two treatments using Cochran-Mantel-Haenszel (CMH) chi-square test. Summary parameter estimates generated from the statistical analyses will be presented by treatment group, and will include the number and proportion of subjects achieving response along with the model estimated odds ratio (including 95% confidence interval) and p-value comparing RHB-104 treatment to placebo. The same sensitivity and exploratory analyses as for primary endpoint analysis will be conducted and summarized.

An additional complementary analysis and summary will be presented for the Proportion of subjects that maintained durable remission at least 3 out of the 4 visits assessed (i.e. $\geq 75\%$ of the visits in remission) week 26 through week 52.

6.3.2.4 Early Remission week 16

Early Remission week 16 will be derived following similar strategy as for the primary endpoint. The summary results will show the number and proportion (%) of subjects experienced early remission (CDAI < 150 score) week 16.

The same statistical approach as for the primary analysis will be employed to compare proportion (%) of subjects experienced Early Remission for the RHB-104 treated group versus Placebo treated group on ITT population using Cochran-Mantel-Haenszel (CMH) chi-square test controlling for the stratification variable anti-TNF agents use (yes/no). Summary parameter estimates generated from the statistical analyses will be presented by treatment group, and will include the number and proportion of subjects in remission along with the model estimated odds ratio (including 95% confidence interval) and p-value comparing RHB-104 treatment to placebo. The same sensitivity and exploratory analyses as for primary endpoint analysis may be conducted and summarized.

6.3.2.5 Steroid free remission week 52

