Table 14.2.2.3.3	Sensitivity Analysis – Durable Remission Week 26 through Week 52: Per-protocol Population
Table 14.2.2.3.4	Sensitivity Analysis - Durable Remission Week 26 through Week 52: Completers Analysis (Observed Cases)
Table 14.2.2.3.5	Exploratory: Durable Remission Week 26 through Week 52 by Treatment Group for Each Baseline Subgroup from Logistic Regression analysis: Intent-to-Treat Population
Figure 14.2.2.3.1	Exploratory: Durable Remission Week 26 through Week 52 Forest Plots by Treatment Group for Each Baseline Subgroup Analysis: Intent-to-Treat Population
Table 14.2.2.4.1	Early Remission Week 16: Intent-to-Treat Population
Table 14.2.2.4.2	Sensitivity Analysis – Early Remission Week 16: Modified Intent-to-Treat Population
Table 14.2.2.4.3	Sensitivity Analysis - Early Remission Week 16: Per-protocol Population
Table 14.2.2.4.4	Sensitivity Analysis - Early Remission Week 16: Completers Analysis (Observed Cases)
Table 14.2.2.4.5	Exploratory: Early Remission Week 16 by Treatment Group for Each Baseline Subgroup from Logistic Regression analysis: Intent-to-Treat Population
Figure 14.2.2.4.1	Exploratory: Early Remission Week 16 Forest Plots by Treatment Group for Each Baseline Subgroup Analysis: Intent-to-Treat Population
Table 14.2.2.5.1	Steroid Free Remission Week 52: Intent-to-Treat
Table 14.2.2.5.2	Sensitivity Analysis – Steroid Free Remission Week 52: Modified Intent-to-Treat Population
Table 14.2.2.5.3	Sensitivity Analysis - Steroid Free Remission Week 52: Per-protocol Population
Table 14.2.2.5.4	Sensitivity Analysis - Steroid Free Remission Week 52: Completers Analysis
Table 14.2.2.5.5	Exploratory: Steroid Free Remission Week 52 by Treatment Group for Each Baseline Subgroup from Logistic Regression analysis: Intent-to-Treat Population
Figure 14.2.2.5.1	Exploratory: Steroid Free Remission Week 52 Forest Plots by Treatment Group for Each Baseline Subgroup Analysis: Intent-to-Treat Population
Supportive/Supplementary Endpoints: Time-to-Event Endpoints	
Table 14.2.3.1.1	Time to Remission: Intent-to-Treat Population
Table 14.2.3.1.2	Duration of Remission: Intent-to-Treat Population
Table 14.2.3.1.3	Time to Response: Intent-to-Treat Population
Table 14.2.3.1.4	Duration of Response: Intent-to-Treat Population
Figure 14.2.3.1.1	Time to Remission Kaplan Meir Survival Curve: Intent-to-Treat Population
Figure 14.2.3.1.2	Duration of Remission Kaplan Meir Survival Curve: Intent-to-Treat Population

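### Does the SAP leave open whether a missed Week 35 or 44 CDAI fails a subject for durable remission?

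*SAP*

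**What the plan says.** The visit schedule (SAP 4.1.1) has CDAI collected at Weeks 26, 35, 44 and 52, so the durable-remission window holds four scores, two of them interim.

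- **SAP 2.2.2** defines the endpoint. A subject fails on any CDAI of 150 or more between Weeks 26 and 52. The definition adds that subjects who "or have no CDAI measurement week 26 or week 52 will be considered not achieved Durable Remission". Weeks 35 and 44 are not named.
- **SAP 6.3.2.3** describes the analysis: "Subjects who are not in remission at any visit point assessment between 26 and 52 weeks will be considered as non-responders for this analysis". It does not mention missed visits. It adds a complementary analysis of subjects who "maintained durable remission at least 3 out of the 4 visits assessed", glossed as at least 75% of visits.
- **SAP 6.1.5** covers diaries and dropouts: "If less than 4 days of diary data is available, the subject will be categorized as a non-responder", with the score then treated as missing. The visit-specific sentences that follow name only Weeks 26 and 52. On dropout: "All patients who prematurely discontinue for any reason will be considered failures for the different proportion based endpoints".
- **SAP 6.1.2** puts durable remission at rank 4, tested at 0.049 two-sided and gating ranks 5 and 6.

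**The concern.** Take a subject who is below 150 at Weeks 26 and 52, stays on study and misses Week 35. Under 2.2.2 no listed failure applies, so the subject is a success on three scores. Under one reading of 6.3.2.3, remission was not shown at every visit, so the subject fails. The short-diary sentence in 6.1.5 is not limited to any visit and points the same way. No sentence says which reading governs.

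At stake is the count for an endpoint under multiplicity control. Near the threshold one subject can decide the test: of 162 per arm, 29 v 16 gives p = 0.037 and 28 v 16 gives p = 0.052. The same subject would then decide whether ranks 5 and 6 are tested.

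The planned sensitivity analyses seem not to isolate the question. SAP 6.3.2.3 says "The same sensitivity and exploratory analyses as for primary endpoint analysis will be conducted and summarized", and for the primary endpoint "The observed case population will include only subjects that have 26 weeks assessment". On that definition, a subject who missed Week 35 or 44 stays in the observed-case set.

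**Working it through.** **Reading the passages together.** The definition in 2.2.2 lists its failures and says which missing visits count. The supportive Week 16–52 endpoint (2.2.3.1) has the same form and names only Weeks 16 and 52. Two parallel definitions that name only the end visits look like a chosen rule. The phrase in 6.3.2.3 refers to a visit assessment, which is naturally one that took place. The diary sentence in 6.1.5 ends by setting the score to missing, which hands the case to the endpoint's own missing-data rule. So 2.2.2 can be programmed as written without contradicting either section.

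**Who is affected.** Dropouts fail under 6.1.5, and subjects given rescue treatment for CD fail under 2.2.1 and 6.1.8. Only subjects who miss an interim visit, stay on study and are below 150 at every attended visit in the window remain.

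**How many.** The documents give no miss rate and no durable-remission rate, so there is no plan figure to reproduce, and what follows is illustrative. Let m be an assumed, independent miss rate per visit, and s the assumed chance that an observed interim CDAI is below 150 in a subject in remission at Weeks 26 and 52.

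- Missing at least one interim score: 1 − (1 − m)².
- Missing both: m².
- Share of 2.2.2 successes that a strict rule would fail: 1 − q², with q = (1 − m)s / [m + (1 − m)s].

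| m | At least one missing | Both missing | Reclassified, s = 1 | Reclassified, s = 0.8 |
|---|---|---|---|---|
| 3% | 5.9% | 0.09% | 5.9% | 7.3% |
| 5% | 9.8% | 0.25% | 9.8% | 12.0% |
| 10% | 19.0% | 1.0% | 19.0% | 22.9% |

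**Effect on the test.** Assume 32 v 16 durable successes of 162 per arm (about 20% v 10%). For a single-stratum Mantel–Haenszel test with t total successes, z = (x₁ − t/2)/√V and V = 162² t(324 − t)/(324² × 323). Here t = 48, V = 10.25, z = 8/3.20 = 2.50 and p = 0.0125. Multiply both counts by q² for s = 0.8, with equal missingness:

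- m = 3%: about 30 v 15, p = 0.016.
- m = 5%: about 28 v 14, p = 0.021.
- m = 10%: 24.67 v 12.34, p = 0.031 unrounded. Whole numbers of 25 v 12 or 24 v 12 give 0.023 or 0.034.

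All are below 0.049.

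**Cost of the strict rule.** Power = Φ[(Δ − z·SE₀)/SE₁], with SE₀ pooled, SE₁ unpooled and z = 1.969 for alpha 0.049. At 20% v 10% and 162 per arm, SE₀ = 0.0397 and SE₁ = 0.0393, so power = Φ(0.558) = 71.1%. Multiplying both rates by q² gives:

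| m | Power, s = 1 | Power, s = 0.8 |
|---|---|---|
| 3% | 68.0% | 67.2% |
| 5% | 65.9% | 64.6% |
| 10% | 60.4% | 58.0% |

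Under the strict rule (s = 1), unequal missingness also drives the result: 5% v 2% per visit (RHB-104 v placebo) gives 59.3% power, and 2% v 5% gives 74.9%.

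**The 3-of-4 analysis.** A subject with three scores, all below 150, passes it on either reading. Passing the main endpoint but failing this looser one requires both interim visits missed and a denominator fixed at four. At m of 3–10% that is m² × 32 = 0.03 to 0.3 subjects in the larger arm. Read as 75% of visits actually assessed, the clash disappears.

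**The case for a change.** The strongest case for a change is that this endpoint belongs to the family meant for labelling claims, so its rule should be explicit before unblinding. The diary sentence in 6.1.5 is unrestricted, and nothing says that 2.2.2 overrides it. Counting a missed interim visit as a failure would match how 2.2.2 treats missing scores at Weeks 16, 26 and 52. The cost would be a few sentences and one table.

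Part of this stands. The rule is inferred rather than stated, and a result within a subject or two of the threshold could turn on it. A clarifying sentence would do no harm.

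It does not establish that the strict rule is needed. Confirming 2.2.2 would remove the doubt equally well, without replacing the most specific definition of the endpoint or giving up power. The gap in the sensitivity sets is also less clear than it looks. The Week 26 definition of observed cases sits in the primary-endpoint section, while SAP 8.1 lists a table titled "Durable Remission Week 26 through Week 52: Completers Analysis (Observed Cases)", and carrying that definition over unchanged is an inference. The per-protocol deviation list in section 5 is open-ended and finalised before unblinding, and 6.2.2 includes non-compliance with study procedures among its categories. Listing 16.2.6.1 gives the CDAI scores by subject, so the count can be repeated under the other rule.

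**Conclusion.** No change follows. This is a gap that an analyst fills sensibly by applying the endpoint definition in 2.2.2: a missed Week 35 or 44 CDAI in a subject who stays on study is not in itself a failure. The stricter alternative is a trade-off. It asks for complete documentation of remission, but it reclassifies about 6–23% of durable successes and lowers power from 71.1% to 58–68%.

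These sizes rest on assumed independent miss rates of 3–10% per visit, interim remission of 80–100%, durable rates of 20% v 10% and 162 per arm. With equal missingness the illustrative conclusion does not move. A reversal would need a result close to 0.049 or missingness that differs between arms, and rank 4 is reached only if ranks 1 to 3 succeed. The supportive Week 16–52 endpoint has the same feature at Weeks 20, 35 and 44: 1 − (1 − m)³ = 8.7%, 14.3% or 27.1% of subjects would lack at least one of those scores. It carries no alpha, so less depends on it.
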